Appendix B Schedule of procedures for participants undergoing neither LN FNA nor leukapheresis

Visit Number	01	02	03	04	05	06	07	08	09	10	11	12	13	14	15
Study Month		0	0.25	0.5	1.5	2	2.25	2.5	3	6	6.25	6.5	7	8	12
Study Week		0	1	2	6	8	9	10	12	24	25	26	28	32	52
Study Day	-56 to 1	1	8	15	43	57	64	71	85	169	176	183	197	225	365
Procedure	Screen ¹	Vac 1				Vac 2			Vac 3						
Study procedures															
Assessment of Understanding		✓													
Informed consent		✓													
Medical history ²		✓													
Physical exam ³		✓	✓	✓	✓	✓	✓	✓	✓	✓	✓	✓	✓	✓	✓
Contraception status assessment ⁴		✓	✓				✓			✓					✓
Risk reduction counseling ⁵		✓	✓		✓	✓				✓	✓	✓	✓	✓	✓
Concomitant medications ⁶		✓	✓	✓	✓	✓	✓	✓	✓	✓	✓	✓	✓	✓	✓
Adverse Events (AEs)			✓	✓	✓		✓	✓	✓	✓	✓	✓	✓	✓	✓
MAAEs/AESIs/SAEs			✓	✓	✓		✓	✓	✓	✓	✓	✓	✓	✓	✓
Vaccination ⁷				✓			✓			✓					
Reactogenicity assessment ⁸				✓			✓			✓					
Social impact assessment			✓	✓	✓		✓	✓	✓	✓	✓	✓	✓	✓	✓
Social impact questionnaire							✓			✓					✓
Clinical labs	Tube								Vol (mL)						
Pregnancy test (urine or serum) ^{9,10}		✓	✓				✓		✓						✓
HBsAg/anti-HCV ¹⁰	SST	5													
HIV screening test ^{10,11}	SST	5													
CBC/Differential ¹⁰	EDTA	5		5				5			5				5
ALT/Creatinine ¹⁰	SST	5		5				5			5				
Storage for additional safety labs ¹²	SST		✓	5	✓			5	✓		5	✓			
HIV diagnostic test	EDTA								10		10			10	20
Research samples¹³															
PBMC for assays and storage	ACD		42.5		42.5		85		144.5		85		204		255
Serum for assays and storage	SST		25.5		25.5		25.5		25.5		25.5		25.5		25.5
Daily volume total (mL)	20	68	15	68		110.5	15	180		120.5	15	229.5		40.5	300.5
56-day total volume (mL)	20	88	103	171		281.5	208.5	373.5		120.5	135.5	365		405.5	300.5

Green shading = Vaccination Visit; Gray shading = FNA visits, which are not applicable to this subgroup

¹ Screening evaluations at Visit 01 are performed no more than 56 days before Day 1.

² Medical history: A complete medical history is performed during screening. At enrollment and at subsequent visits, an interim medical history may be performed.

³ A complete **physical exam** is performed at screening and last clinic visit, to include height, weight, vital signs, and clinical assessments of head, ears, eyes, nose, and throat; neck, lymph nodes; heart; chest; abdomen; extremities; neurological function; and skin. At other visits, a **targeted physical exam** will be performed as needed, based on participant report or indications of illness.

⁴ Contraception status assessment is required only for participants who were assigned female sex at birth and are capable of becoming pregnant.

⁵ Risk reduction counseling per CRS Standard Operating Procedures.

⁶ Concomitant medications, including prescription and non-prescription drugs, vitamins, topical products, alternative/complementary medicines, recreational drugs, vaccinations, and allergy shots are recorded during screening, at enrollment, and at each subsequent clinic visit.

⁷ Vaccination (in clinic assessments): At least 30 minutes after each vaccination and prior to clinic discharge, participants will have vital signs taken, the injection site will be assessed, and systemic symptoms will be assessed.

⁸ Reactogenicity: Clinic staff will follow new or unresolved reactogenicity symptoms present at day 7 until resolution.

⁹ Pregnancy test: For participants assigned female sex at birth. Pregnancy test may be performed on urine or blood specimens. Persons who are NOT capable of becoming pregnant due to total hysterectomy or bilateral oophorectomy (verified by medical records), or menopause (no menses for ≥ 1 year) are not required to undergo pregnancy testing. Persons who are confirmed pregnant, pregnancy testing is not required, unless clinically indicated.

¹⁰ Local labs may assign appropriate alternative tube types for locally performed tests.

¹¹ HIV screening test: see Section 5.1.1.

¹² For additional assays to be performed if clinically indicated (See Section 8.4)

¹³ Research samples: Blood draw volumes for each tube type shown.

y=SST blood collected for assays and serum storage will also cover specimen needs for storage for additional safety labs; no separate blood draw is needed.

Appendix C Schedule of procedures for extended follow-up for participants with unresolved study product-related urticaria-associated symptoms

Visit Number	101	102	103	104	105	106	107	108	Urticaria-Associated Symptom Visit ⁴
Study Month	15	18	21	24	30	36	48	60	
Study Week	65	78	91	104	130	156	208	260	
Study Day	456	547	638	729	911	1093	1457	1821	
Study procedures									
Informed consent		✓							
Urticaria-related symptom questionnaire		✓	✓	✓	✓	✓	✓	✓	✓
Medical history ¹		✓	✓	✓	✓	✓	✓	✓	✓
Concomitant medications ²		✓	✓	✓	✓	✓	✓	✓	✓
Dermatological Adverse Events (AEs)		✓	✓	✓	✓	✓	✓	✓	✓
SAEs		✓	✓	✓	✓	✓	✓	✓	✓
Targeted Physical exam (if clinically indicated) ³		✓	✓	✓	✓	✓	✓	✓	✓
Research samples									
Serum for storage and assays ⁴	SST	0	17	As clinically indicated and at the participant's exit visit ⁴				17	17
Daily volume total (mL)	0	17	0	0	0	0	0	17	17
56-day total volume (mL)	0	17	0	0	0	0	0	17	

¹ **Medical history:** Based on the responses on urticaria-related symptom questionnaire, an interim medical history may be performed and documented in the participant's chart.

² **Concomitant medications**, including review of prescription and non-prescription drugs, vitamins, topical products, alternative/complementary medicines, recreational drugs, vaccinations, and allergy shots are updated and any new information is recorded at each contact.

³ Site may ask the participant to come in for a targeted (abbreviated) **physical exam** if during the remote visit, the participant reports anything that may require further evaluation. See Section 8.6.

⁴See Section 8.6. Participants in extended follow will have clinic visits to collect 17 mls serum for banking at Visit 102, their exit visit, and at any clinic visit(s) scheduled to further evaluate urticaria-associated symptoms.

Appendix D Visit windows for main study

Visit Number	Visit Type	Lower Allowable Window (-)	Lower Target Window (-)	Target Day ¹	Upper Target Window (+)	Upper Allowable Window (+)
01.0	Screening	-56	-		-	Up to Day 1
02.0	Enrollment/Vaccination 1	-	-	1	-	-
03.0	1 week post-vaccination 1		-3	8	+2	
04.0	2 weeks post-vaccination 1		-4	15	+4	+7
05.0**	6 weeks post-vaccination 1 FNA	-7	-4	43	+4	+7
06.0	Vaccination 2	-7	-4	57	+4	+7
07.0	1 week post-vaccination 2		-3	64	+2	
08	2 weeks post-vaccination 2	-	-4	71	+4	+7
	Leukapheresis		-4	71	+1	+4
09.0**	4 weeks post-vaccination 2 FNA	-7	-4	85	+4	+7
10.0	Vaccination 3	-21	-14	169	+14	+21
11.0	1 week post-vaccination 3		-3	176	+2	
12.0	2 weeks post-vaccination 3 Primary Immunogenicity		-4	183	+4	+7
	Leukapheresis		-4	183	+1	+4
13.0**	4 weeks post-vaccination 3 FNA	-7	-4	197	+4	+7
14.0	8 weeks post-vaccination 3	-14	-7	225	+7	+14
15.0	Final Visit	-28	-14	365	+14	+28

Green shading = Vaccination Visit; Blue shading = FNA visit

* All target dates are relative to Day 1, with the exception of the post-vaccination visits (visits 3.0-5.0, 7.0-9.0, and 11.0-14.0) which are relative to the vaccination immediately preceding the visit.

** Visits 5.0, 9.0, and 13.0 are only required for participants who are providing lymph node FNA collections.

Appendix E Visit windows for follow-up of participants with unresolved study product-related urticaria-associated symptoms

Visit Number	Visit Type	Lower Allowable Window (-)	Lower Target Window (-)	Target Day*	Upper Target Window (+)	Upper Allowable Window (+)
101	Initial contact	-42	-28	456	+28	+42
102	1.5-year contact	-42	-28	547	+28	+42
103	1.75-year contact	-42	-28	638	+28	+42
104	2-year contact	-42	-28	729	+28	+42
105	2.5-year contact	-84	-56	911	+56	+84
106	3-year contact	-84	-56	1093	+56	+84
107	4-year contact	-84	-56	1457	+56	+84
108	Final 5-year contact	-84	-56	1821	+56	+84

* All Target Days are relative to Day 1 of the main study (enrollment date); informed consent for follow-up can be collected any time prior and up to Visit 101

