2.4 Rationale for Schedule

To match the schedule used in other comparable trials and pre-clinical studies, BG505 MD39.3 HIV Trimer mRNA vaccines will be administered at a dose of 100 mcg or 250 mcg at Month 0, 2 and 6. Rabbit studies described above demonstrated that autologous neutralizing antibody responses were significantly increased following the third compared with the second vaccine administration timepoint. A similar experimental mRNA vaccine being evaluated for Cytomegalovirus (CMV), the Moderna mRNA CMV vaccine (mRNA-1647), is administered at Month 0, 2 and 6. Neutralizing antibody titers increased following the Month 2 vaccination, were further boosted after the Month 6 vaccination and were then sustained for at least 12 months (24-26).

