3.2 Secondary objectives and endpoints

Secondary objective 1:

To evaluate the ability of BG505 MD39.3 trimer mRNA vaccines to elicit humoral and cellular immune responses and to compare responses between the membrane-bound vaccine regimen (BG505 MD39.3 gp151 mRNA) and the membrane-bound knockout (BG505 MD39.3 gp151 CD4KO mRNA) and between the membrane-bound vaccine regimen (BG505 MD39.3 gp151 mRNA) and the soluble trimer (BG505 MD39.3 mRNA) vaccine arms, within each dose level and to compare responses between dose levels for each vaccine regimen

Secondary endpoints 1:

- Occurrence, magnitude, and response rate of serum antibody neutralization of a vaccine-matched tier 2 HIV-1 strain as measured by the TZM-bl assay two weeks after the second vaccination
- Occurrence, magnitude, and response rate of serum IgG binding antibodies to the BG505 trimer, and specific epitopes (base of trimer, V3, internal epitope) as measured by binding antibody multiplex assay (BAMA) two weeks after the second and third vaccination
- Occurrence, magnitude, and response rate of CD4+ T-cell responses as assessed by intracellular cytokine staining assays (ICS) two weeks after the third vaccination

Secondary objective 2:

To evaluate the durability of humoral immune responses to BG505 MD39.3 trimer mRNA vaccines and to compare durability between arms

Secondary endpoints 2:

- Occurrence, magnitude, and response rate of serum antibody neutralization of a vaccine-matched tier 2 HIV-1 strain, as measured by the TZM-bl assay six months after the third vaccination
- Occurrence, magnitude, and response rate of serum IgG binding antibodies to the BG505 trimer, and specific epitopes (base of trimer, V3, internal epitope), as measured by BAMA six months after the third vaccination

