6.3.4 Immunogenicity analyses

6.3.4.1 General approach

For the statistical analysis of immunogenicity endpoints, data from enrolled participants will be used according to the initial randomization assignment regardless of how many injections they received. Additional analyses may be performed, limited to participants who received all scheduled injections per protocol. Assay results that are unreliable are excluded; results from specimens collected outside of the visit window, or from HIV-infected participants post-infection, may be excluded. Since the exact date of HIV infection is unknown, any assay data from blood draws 4 weeks prior to an infected participant's last seronegative sample and thereafter may be excluded. If an HIV-infected participant does not have a seronegative sample postenrollment, then all data from that participant may be excluded from the analysis.

Discrete categorical assay endpoints (eg, response rates) will be analyzed by tabulating the frequency of positive response for each assay by antigen and treatment arm at each timepoint for which an assessment is performed. Crude response rates will be presented with their corresponding 95% confidence interval estimates calculated using the score test method (40). Barnard or Fisher's exact tests, as specified in the SAP, will be used to compare the response rates of any 2 vaccine arms, with a significant difference declared if the 2-sided p-value is ≤ 0.05 . In general Barnard's is preferred since under most circumstances it is more powerful than Fisher's exact test (41).

For quantitative assay data (eg, percentage of positive cells from ICS assay), graphical and tabular summaries of the distributions by antigen, treatment arm, and timepoint will be made. For all primary and secondary immunogenicity endpoints, box plots and plots of estimated reverse cumulative distribution curves will be used for graphical display of all of the study arms. Typically, the results will be shown for each vaccine arm.

The difference between arms at a specific timepoint will be tested with a nonparametric Wilcoxon rank sum test if the data are not normally distributed and with a 2-sample t-test if the data appear to be normally distributed. The primary

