If a substantial amount of immunogenicity data are missing for an endpoint (at least 1 value missing from more than 20% of participants), then using the methods that require the MCAR assumption may give misleading results. In this situation, analyses of the immunogenicity endpoints at a specific timepoint will be performed with methods such as targeted minimum loss-based estimation (TMLE), parametric generalized linear models fit by maximum likelihood, augmented inverse probability weighting (AIPW) methods or multiple imputation methods. TMLE and AIPW are typically preferred because they are doubly robust, providing consistent estimation and appropriate inferences if either the outcome regression or the probability of observing the response value are modeled correctly, under the assumption that the missing data are missing at random (MAR). MAR assumes that the probability of an observation being missing only depends upon the observed responses and upon observed covariates, but not upon any unobserved data. TMLE methods will typically be implemented with the drtmle R package (46) available at CRAN, and will entail specification of a library of learners for the outcome regression and for the probability of observing the response value. When data are not missing at random, sensitivity analyses may be performed as an exploratory analysis. For assessing repeated immunogenicity measurement, linear mixed effects models will be used. If the immunological outcomes are left- and/or right- censored, then the linear mixed effects models of Hughes (47) will be used, because they accommodate the censoring. In addition, secondary analyses of repeated immunogenicity measurements may be done using weighted GEE (48) methods, which are valid under MAR. All of the models described above in this paragraph will include as covariates all available baseline predictors of the missing outcomes.

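### Does windowing the durability visit from Day 1, and not from the third vaccination, undermine the six-month durability comparison?

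*Protocol*

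**What the plan says.** Protocol 3.2 defines the durability endpoints as neutralization "as measured by the TZM-bl assay six months after the third vaccination" and binding antibody "as measured by BAMA six months after the third vaccination", with durability compared between arms.

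The Appendix D footnote says: "All target dates are relative to Day 1, with the exception of the post-vaccination visits (visits 3.0-5.0, 7.0-9.0, and 11.0-14.0"), and ties those excepted visits to the dose just before them. Vaccination 3 (Visit 10, Day 169, target ±14, allowable ±21) and the final visit (Visit 15, Day 365, target ±14, allowable ±28) are not excepted, so each is windowed from Day 1.

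Protocol 6.3.4.1 gives the analysis:

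- "The difference between arms at a specific timepoint will be tested with a nonparametric Wilcoxon rank sum test" if the data are not normal, and otherwise with a t-test.
- Exclusion is allowed for "results from specimens collected outside of the visit window".
- "data from enrolled participants will be used according to the initial randomization assignment regardless of how many injections they received".
- "For assessing repeated immunogenicity measurement, linear mixed effects models will be used"; no time scale is named.

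The closing text of Protocol 6.3.4.2 leaves the detail of each assay's analysis to a statistical analysis plan. The SAP reviewed here covers safety data only (SAP section 2).

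**The concern.** The endpoint's clock starts at dose 3 and the visit's clock starts at enrollment. Two participants who both comply fully can give their six-month sample up to 245 - 147 = 98 days apart, measured from dose 3. If titers halved every 30 days, that gap alone would be worth 2^(98/30) = 9.6-fold. Excluding out-of-window specimens does not touch this spread, because all of it lies inside the windows. The two-sample tests have no term for elapsed time.

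Two things would be at stake. One is added noise in the randomized comparisons within a dose level. The other is possible bias in comparisons between dose levels, if the typical interval differed between Part A and Part B.

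**Working it through.** **1. The plan's own days.** Appendices A and B place vaccination 3 at Week 24 and the final visit at Week 52. With study day = 7 × week + 1, these are 7 × 24 + 1 = 169 and 7 × 52 + 1 = 365, as printed. The nominal interval is 365 - 169 = 196 days. Six calendar months are 6 × 30.4375 = 182.6 days, so the nominal interval is already about 13 days longer. The schedule labels these visits Months 6 and 12, and on that scale the interval is six months.

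**2. Range with both visits in window.**

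| Windows | Shortest | Longest | Width |
|---|---|---|---|
| Target | (365 - 14) - (169 + 14) = 168 | (365 + 14) - (169 - 14) = 224 | 56 days |
| Allowable | (365 - 28) - (169 + 21) = 147 | (365 + 28) - (169 - 21) = 245 | 98 days |

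**3. How often the extremes occur.** Assume, since the documents give no distribution, that both dates are independent and uniform over the allowable windows. The chance of lying more than 28 days from 196 is (49 - 28)²/(2 × 42 × 56) = 441/4704 = 9.4% on each side. About 81% of intervals therefore fall within 168-224 days.

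**4. Spread.** The SD of the interval is √((42² + 56²)/12) = 20.2 days. The dose-3 window supplies 42²/(42² + 56²) = 36% of the variance; the other 64% is Visit 15's own window. Anchoring Visit 15 to dose 3 with the same window width would leave 56/√12 = 16.2 days.

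**5. Effect on detectable differences.** Protocol 6.1.1 gives SDs of 0.85 (log10 ID50) and 0.23 (binding, from rabbit ELISA AUC). For n = 15 per arm, a two-sided t-test at 0.05 and 90% power, the detectable fold is 10^(1.226 × SD). This gives 11.0 and 1.91, matching the protocol's 11-fold and 1.9-fold. Timing adds a log10 SD of (SD in days) × 0.30103/half-life, combined as √(SD² + added²). Half-lives of 30 and 120 days are assumptions.

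| Half-life | Added SD, as planned | ID50 as planned | ID50 re-anchored | Binding as planned | Binding re-anchored |
|---|---|---|---|---|---|
| 120 days | 0.051 | 11.07 | 11.05 | 1.94 | 1.93 |
| 30 days | 0.203 | 11.79 | 11.51 | 2.38 | 2.21 |

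**6. Which end is plausible.** Visits 12 and 15 are nominally 196 - 14 = 182 days apart. A constant 30-day half-life implies a fall of 2^(182/30) = 67-fold between them, against 2^(182/120) = 2.9-fold at 120 days. Protocol 2.4 says that titers for another mRNA vaccine on the same schedule "were further boosted after the Month 6 vaccination and were then sustained for at least 12 months". That is a different antigen and not a half-life, but it points to slow decay.

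**7. Cost of re-anchoring.** The latest in-window Visit 15 would move from Day 365 + 28 = 393 to Day 190 + 196 + 28 = 414. That is the day Visit 101 of the extended follow-up can open (456 - 42 = 414). A dose 3 given on Day 191 would carry it to Day 415, inside that window.

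**The case for a change.** The strongest argument for acting concerns comparisons between dose levels. Parts A and B are randomized separately and enroll partly at different sites and times (Protocol 6.2 and 9.6), and a safety pause can hold vaccinations in one dose level (Protocol 9.7). If dose 3 ran late in one Part, that Part would be sampled sooner after it and would look more durable. As an illustration only, a mean shift of 14 days gives 2^(14/120) = 1.08-fold to 2^(14/30) = 1.38-fold. A difference between Parts in Visit 15 timing would act in the same way. Recording elapsed days costs almost nothing, since the dates are already collected.

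Part of this stands. The interval could differ between Parts, and a reader of a between-dose durability result would want to see it. But the documents schedule no such delay: the planned sentinel holds stop enrollment after the first dose and do not postpone dose 3. The illustrated shift is also below the protocol's own detectable differences of 1.9-fold and 11-fold, and the between-Part comparison is not randomized in any case. A model in actual days has its own limits. It is undefined for participants who never received dose 3, it conditions on something that happened after randomization, and it needs a reference day (183 or 196, for example) before it estimates durability at six months. It could therefore only support the analysis of all enrolled participants.

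**Conclusion.** The different clocks are a fact, and the ranges of 168-224 and 147-245 days are correct. No change is needed. The planned comparisons within a dose level remain sound: the arms are randomized, share the same windows, and differ in timing only by chance unless a single group is paused. The cost in precision is negligible for neutralization (11.07-11.79-fold against 11.0). For binding it is small unless decay is fast (1.94-2.38-fold against 1.91). At the more plausible slow end, re-anchoring would gain 0.02-fold for ID50 and 0.01-fold for binding.

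Anchoring the final visit to Day 1 is a fair trade-off. It gives everyone the same 12-month safety follow-up, including participants who miss dose 3, and fixes when extended follow-up is triggered. The unstated time scale of the mixed models is a gap that an analyst would fill sensibly, most simply by using actual days and tabulating them by arm. The absence of this detail from a safety-only SAP does not show that elapsed time will be ignored.

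The sizes rest on assumed half-lives of 30 to 120 days, uniform timing within the windows, the protocol's rabbit SDs standing in for human values, and n = 15. That n reflects the 15% missing data the protocol expects at Month 6.5, and missingness could be higher at Month 12. Response rates were not calculated separately. The primary endpoint is not affected.

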Appendix H Low risk guidelines for US

The following are intended as guidelines for the investigator to help identify potential vaccine trial participants at “low risk” for HIV infection. These guidelines are based on behaviors within the last 6-12 months prior to enrollment; however, it may be appropriate to consider a person’s behavior over a longer period of time than specified to assess the person’s likelihood of maintaining low risk behavior. *Some volunteers may not be appropriate for enrollment even if they meet these guidelines.* These guidelines should be supplemented and interpreted with local epidemiologic information about HIV prevalence in your area and community networks. The investigator may review the risk level of any volunteer with the site PI and/or the Protocol Safety Review Team.

A volunteer may be appropriate for inclusion if he/she/they meets these guidelines:

A. For US volunteers NOT on stable Pre-exposure prophylaxis (PrEP)

1. SEXUAL BEHAVIORS

In the **last 12 months** did not:

- A. Have oral, vaginal or anal intercourse with an HIV-infected partner, or a partner who uses injection drugs
- B. Give or receive money, drugs, gifts or services in exchange for oral, vaginal or anal sex

AND

In the **last 6 months** has abstained from penile/anal or penile/vaginal intercourse, OR

In the **last 6 months** had 4 or fewer partners of the opposite birth sex for vaginal and/or anal intercourse, OR

Is an MSM (person born male with partner(s) born male) who, in the **last 12 months**:

- Had 2 or fewer MSM partners for anal intercourse and had no unprotected anal sex with MSM, OR
- Had unprotected anal intercourse with only 1 MSM partner, within a monogamous relationship lasting at least 12 months (during which neither partner had any other partners). If the monogamous relationship ended, the volunteer may then have had protected anal intercourse with 1 other MSM partner (total 2 or fewer partners in the last 12 months), OR

Is a transgender person, regardless of the point on the transition spectrum, having sex with men (born male) and/or other transgender persons, who in the **last 12 months**:

- Had 2 or fewer partners for anal or vaginal intercourse, and had no unprotected anal or vaginal sex, OR
- Had unprotected anal or vaginal intercourse sex with 1 partner only within a monogamous relationship lasting at least 12 months (during which neither partner had any other partners). If the monogamous relationship ended, may then have

had protected anal or vaginal sex with 1 other partner (total 2 or fewer partners in the last 12 months).

AND

Uses or intends to use condoms in situations which may include penile/anal or penile/vaginal intercourse with new partners of unknown HIV status, occasional partners, partners outside a primary relationship, and/or partners known to have other partners.

